The ELISA test for *C. trachomatis* and culture for *N. gonorrhoeae* proved very difficult to establish in some of the regional, government-run laboratories. A central laboratory was therefore established in Lima before the intervention began at the U.S. Naval Medical Research Detachment, and had to be relocated twice thereafter, first to the Peru National Institute of Health, later to a new laboratory at UPCH. The initial choice of centralized Roche AMPLICOR PCR testing, was followed by growing international evidence for non-specificity of this test for *N. gonorrhoeae*—a problem made more serious by the unexpectedly low prevalence of *N. gonorrhoeae*, further contributing to low positive predictive value of positive PCR tests.

Subsequent additional funding from USAID and NIH early in the intervention trial, and from the Wellcome Trust after the recommendations from the 2006 DSMB meeting, also further allowed us to substantially strengthen the intervention in the ten intervention cities by:

- Introduction of a health communication campaign to promote STD symptom recognition and appropriate early health-care seeking
- Social marketing in the intervention cities of a) dual purpose condoms for STD prophylaxis as well as contraception, and b) STD treatment packets marketed to pharmacies for treatment of urethral discharge in men and vaginal discharge in women
- During the last nine months of the intervention, the assessment in the intervention cities of the feasibility of mobile team outreach to male sex workers having commercial sex with men

- Also during the last nine months of the intervention, implementation of rapid point of care syphilis testing in both female and male sex workers
- Addition of HIV, HSV, HTLV, and hepatitis B serologic tests as secondary outcome measures, or for assessment of the prevalence of these sexually transmittable infections, or both
- Addition of Gen-Probe APTIMA NAAT testing of vaginal swab and male urine specimens from stored specimens from the 2002-03 baseline survey, and from the 2006 outcome surveys for *T. vaginalis*, allowing us to replace *T. vaginalis* culture with *T. vaginalis* NAAT tests as an outcome measure; and use of APTIMA assays allowed us to undertake confirmatory testing of specimens from participants classified as positive for *N. gonorrhoeae* or *C. trachomatis* by Roche AMPLICOR PCR testing.

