Counseling to pharmacy clients with STD: For men with a syndrome suggesting urethritis, women with symptoms of abnormal discharge, and for men and women with symptoms of genital ulcer disease seen in pharmacy settings, we adapted a promising client-centered intervention, pilot-tested a motivational interviewing training program with pharmacy workers in Lima, and developed a training video for STD/HIV prevention. The client-centered counseling primarily assesses the client's actual and perceived risk, reduces barriers to risk reduction, and supports behavior change and promotes partner treatment. These objectives reflect the 4 C's of syndromic management for STD: enhancing compliance; counseling for risk reduction; promoting condoms for high risk sex; and sexual contact referral and treatment. Treatment of vaginal discharge with metronidazole 2 g single dose aimed to cure trichomoniasis, and counseling was reinforced at the pharmacy level. Training pharmacy workers to recognize possible cases of PID and genital ulcer disease was also linked to training the workers to refer such cases for management to the members of the PREVEN Network.

STD symptoms recognition and early health care-seeking campaignJ: This health communication campaign, carried out by the PREVEN team in each of the intervention cities, employed pamphlets, posters, local media, radios and local TV stations, with leaders from the PREVEN network and local authorities involved in the process. The main objectives of the campaign included recognition of urethral discharge as an STD and vaginal discharge as possibly an STD and knowledge of the resources for information (web page, trained pharmacies) and treatment (members of the PREVEN network).

---

J The Health Communication Campaign, on early STD symptom recognition and early healthcare-seeking from appropriate providers, was initiated in 2003 and continued, after a short pause, through August 2005. See Section V. Timeline.

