## DATA COLLECTION

### **General Population Survey**

#### **Interview**

Participants responded to a face-to-face questionnaire administered by the interviewer. The questionnaire addressed data on demographic and household characteristics, travel, migration, labor, health seeking behavior, marriage, contraception, knowledge about STDs and reproductive health. Afterwards, the participants responded to a self-administered questionnaire, exploring characteristics of the participant's sexual behavior.T A GPS Interviewers Manual of Procedures (MOP) provided detailed instructions to guide and standardize all study procedures across sites; it was changed in 2005 and 2006 to include the collection of data with PDAs.

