
awareness about STD symptom recognition and to promote the RED PREVEN network. An initial assessment and pilot testing resulted in the following key messages:

- Four out of 10 men and 5 out of 10 women have an STD without knowing it. STDs affect us all. Get information!
- (For men) “Pus from your penis or a burning sensation when you urinate is an STD. Get help from a RED PREVEN member”
- (For women) “Abnormal vaginal discharge - if you are sexually active and you have an increase in the amount vaginal discharge or a different odor or color, it could be an STD. Get help from a RED PREVEN member”
- RED PREVEN: We know about STDs. Look for the RED PREVEN sign in pharmacies, boticas and clinicians’ offices.

Across the country, campaign activities included: promoting the key messages in the media, distributing merchandise and educational materials, and hosting educational workshops for parents, health workers and governmental authorities. As part of implementation efforts, we established formal collaboration agreements with key stakeholders in each city, which helped to form local STD task forces and community partnerships. For example, we partnered with a professional group of “mototaxistas” (a “mototaxi” is a small vehicle, similar to motorcycle, with a carriage on the back to carry 2-3 passengers). The drivers distributed STD prevention materials to their clients, which was particularly helpful in hard to reach areas. Pharmacy owners provided in-kind support by paying to have the materials reprinted. Media outlets in the different cities offered space in newspapers and programming time during radios and local TV broadcasts to present the campaign messages and conduct interviews of RED PREVEN members.

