Sexfswnocondom	How many times sex w/ prostitute w/o condom in last 12 months	GPS SA Q2.10 (males who gave response of 1 or more to 'sexfswnocondom');	1-4=actual #; 5=more than 4; 6=Always uses condom; 66=Doesn't remember	
Nocondc	Noncondom use w/ prostitute in last 12 months (men only):	Created variable Omission in code creating variable for interim analysis caused rates to be dramatically overestimated; See note.	1=yes (had sex with prostitute without condom in last year); 0=no (always used condom or no sex with prostitute)	Outcome

Sexmsm	Sex with male	GPS SA Q2.11 (males only)		
Msmnum	How many times sex w/male	GPS SA Q2.14 (males only, but variable "msmnum" received at interim analysis shows everyone responding to this including women and men who did not acknowledge MSM. Looks like not correct data for this question.)	0=None 1-4=? 66=Doesn't remember	
Msmnocond	How many times sex w/male w/o condom	GPS SA Q2.15 (males only, and those who acknowledge MSM.)	1-4=actual #; 5= more than 4; 6=Always uses condom; 66=Doesn't remember	
Nocondm	Noncondom use with male in last 12 months (men only)	Created variable Omission in code creating variable for interim analysis was an oversight and led to overstating rates; see note.	1=yes (had sex with male without condom in last year); 0=no (always used condom or no sex with male)	Outcome
Sexlastpartnum	Number of times sex with last partner in last 3 months	GPS SA Q3.11	1-20=actual # 21=more than 20; 66=doesn't remember	
Sexlastpartnocondom	Number of times sex with last partner in last 3 months without condom	GPS SA Q3.12	1-20=actual # 21=more than 20; 22=always uses condom; 66=doesn't remember	
Nocondl	Noncondom use w/last partner (GPS)	Created variable	1=yes (had sex with last sex partner without condom in last year); 0=no (always used condom or no sex in last 3 months)	Outcome
hlthseek	Health seeking behavior – "If you had abnormal secretion ... what would you do first?"	GPS SA Q2.1	=Nothing =Consult friend =Pharmacy =Doc/Clinic =Hospital =Meds @ home =Other	
Workplace	Workplace type for	FSW questionnaire Q503 (last 7 days)	1=Brothel;	covariate

	FSW	or Q504 (last month)	2=Nightclub; 3=Bar; 4=Street; Other 99=no response	
Culinter	Condom use w/ last intercourse (FSW)	FSW questionnaire Q618 (is this only among women whose last sex was vaginal intercourse? – Q617?)	1=Yes 2=No (I created 'cl', same variable but 0=no/1=yes)	Outcome

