#### *Secondary analysis*

The analysis outlined above will also be used for the following endpoints:

- **combsti** in FSW
- **Ctresul, ggresul, newsyph, tvresul, HIVresul, BV** in GPS
- **Ctresul, ggresul, newsyph, tvresul, HIVresul, BV** in FSW
- **Nocondl** in GPS
- **Culinter** in FSW

To determine if the intervention is more effective in particular subsets of individuals (i.e. those who prefer to use pharmacies for treatment of STI-related symptoms) we will use an individual level analysis of the 2006 GPS data based on the following model

$$\text{logit}(p_{ij}) = b_0 + b_1 T_i + b_2 B_i + b_3 X_{ij} + b_4 T_i X_{ij} + a_i$$

where  $T_i$  is a 0/1 treatment indicator for city  $i$ ,  $B_i$  is the baseline disease prevalence for city  $i$ ,  $X_{ij}$  is a 0/1 covariate indicating whether subject  $j$  in city  $i$  belongs to the subset of interest (i.e. uses FSW) and  $a_i$  is a random city effect ( $a_i \sim N(0, \sigma^2)$ ). The outcome in this analysis will be **combsti**. In the absence of the interaction term, the  $b_1$  coefficient from this model estimates the overall treatment effect (comparable to  $b_0$  in model H1). With the interaction term in the model, the hypothesis  $H_0: b_4 = 0$  will be used to test if the intervention effect on **combsti** differs across levels of  $X$  (e.g. we might expect  $b_4$  to be positive – intervention more effective – in individuals who prefer to use pharmacies for treatment of STI-related symptoms). A two-sided 0.05 level test will be used.

- To determine if the effectiveness of the intervention differs in individuals who prefer to use pharmacies for STI-related symptoms,  $X_{ij} = \mathbf{hlthseek}$ .
- To determine if the effectiveness of the intervention differs in men who use FSW,  $X_{ij} = \mathbf{sexfsw}$  and the analysis is restricted to men

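### The pharmacy-preference subgroup is defined by a 2006 answer that the intervention may have changed, so the interaction test may mix a difference in effect with a change in who is in the subgroup

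*Supplement*

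**What the plan says.** In the latest PREVEN Trial Data Analysis Plan, under Secondary analysis, the plan states for its subgroup questions: "we will use an individual level analysis of the 2006 GPS data based on the following model". The model is a logistic regression with a treatment indicator T, the city's baseline prevalence, a 0/1 subgroup covariate X, the product of T and X, and a random city effect. The null hypothesis is that the product coefficient b4 is zero, and "A two-sided 0.05 level test will be used".

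The pharmacy question is stated as "To determine if the effectiveness of the intervention differs in individuals who prefer to use pharmacies for STI-related symptoms", and for it X is hlthseek. The Variables table defines it as the self-administered item "If you had abnormal secretion ... what would you do first". Pharmacy is one of seven listed answers.

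The Protocol Summary describes what the intervention cities received. Its introduction lists "Introduction of a health communication campaign to promote STD symptom recognition and appropriate early health-care seeking". Intervention Modality 1 says that the campaign ran in each of the intervention cities, concerned urethral and vaginal discharge, and aimed among other things at "knowledge of the resources for information (web page, trained pharmacies) and treatment (members of the PREVEN network". The trial summary presented to the DSMB (section 2.1) gives the public message "Look for the RED PREVEN sign in pharmacies, boticas and" clinicians' offices. According to the section on prevention activities in control cities, the trial provided no such campaign and no pharmacy training there.

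**The concern.** Randomisation makes the two arms comparable as a whole. It does not make subgroups comparable when they are formed after treatment has started, by something that treatment can alter. Here X is recorded more than three years after the July 2003 start, and the question is about the symptom that the campaign addressed.

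The surveys are separate cross-sections without follow-up of individuals, so nobody's earlier preference is known. If the campaign or the pharmacy network changed where people say they would go first, the pharmacy group in intervention cities holds a different mix of people from the pharmacy group in control cities. The coefficient b4 then carries that difference in mix together with any real difference in effect.

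At stake is a stated secondary aim with its own 0.05-level test. A rejection could be read as evidence that the programme works better, or worse, in pharmacy users when it does not. A real difference could also be cancelled. The plan has no check that would reveal this. Its list of descriptive tables contains no table of hlthseek by arm, and the behavioural dummy table attached to the other plan version in the supplement shows pharmacy use by gender only.

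**Working it through.** The documents give no power, effect size or hlthseek distribution for this test, so there is no stated figure to reproduce. What can be shown is how far a shift in membership alone would move b4.

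**Inputs from the documents.** Composite prevalence in the general population is 0.10 (power table, any STD). There are 500 results per city and 10 cities per arm, hence 5,000 per arm.

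**Assumptions, not in the documents.**
- X = 1 means that the answer is pharmacy.
- Without the campaign, 30% prefer pharmacies.
- Prevalence is 10% in both subgroups of the control cities.
- The intervention has no effect on infection.
- In intervention cities a share *s* of the population moves into the pharmacy group, and these people have prevalence *p*.

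**Formulas for intervention cities.**
- Pharmacy group: (0.30 × 0.10 + s·p) / (0.30 + s)
- Other group: (0.70 × 0.10 − s·p) / (0.70 − s)
- Spurious interaction OR: odds in the pharmacy group divided by odds in the other group. The control-city ratio is 1.

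**Example, s = 0.10 and p = 0.05.** Pharmacy: (0.030 + 0.005)/0.40 = 8.75%. Other: (0.070 − 0.005)/0.60 = 10.83%. OR = (0.0875/0.9125) / (0.1083/0.8917) = 0.79, so b4 = −0.237.

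The standard error, ignoring the city random effect, is the square root of the sum of 1/[n·π(1−π)] over the four arm-by-subgroup cells, where n and π are the number and prevalence in the cell. The n are 1,500 and 3,500 in control cities, and 2,000 and 3,000 in intervention cities in this example. This gives 0.1425 and z = −0.237/0.1425 = −1.66. The chance of rejecting at two-sided 0.05 is then about 38%.

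| s | p | Pharmacy | Other | Spurious OR | Rejection at nominal 5% |
|---|---|---|---|---|---|
| 0.10 | 0.05 | 8.75% | 10.83% | 0.79 | 38% |
| 0.10 | 0.07 | 9.25% | 10.50% | 0.87 | 17% |
| 0.10 | 0.10 | 10.00% | 10.00% | 1.00 | 5% |
| 0.10 | 0.13 | 10.75% | 9.50% | 1.15 | 17% |
| 0.15 | 0.05 | 8.33% | 11.36% | 0.71 | 68% |
| 0.15 | 0.13 | 11.00% | 9.18% | 1.22 | 30% |

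If people move out of the pharmacy group instead, the sign reverses. With 10 points moving out at prevalence 5%, the pharmacy group shows (0.030 − 0.005)/0.20 = 12.5% and the other group (0.070 + 0.005)/0.80 = 9.375%, an OR of 1.38. With no movement, or in this setting with movers of average risk, there is no bias. An overall intervention OR of 0.7 in place of 1 leaves the spurious b4 nearly unchanged (−0.235 against −0.237 in the worked example).

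**The case against.** The strongest reply is that movement between the groups has not been shown. No section reports hlthseek by arm, and no section sets a goal of drawing people from clinics to pharmacies. The campaign pointed to clinicians as well. Moving from an untrained to a trained pharmacy leaves X unchanged. The communication campaign ended in August 2005, before the 2006 survey. The DSMB trial summary also describes campaign activities as running across the country, so exposure in one arm only is not certain. The milder cases above are about one standard error, and every shift and prevalence is assumed.

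Most of this stands, and it limits the claim. A reader might infer that the campaign did move people into the pharmacy group in one arm, or that the interaction is biased in a known direction. The documents support neither reading. Net movement could be in, out or nil.

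The reply does not remove the problem. An unknown direction makes b4 harder to interpret. The pharmacy network continued after August 2005. One could argue that pharmacies were promoted for information only and network members for treatment, but the Protocol Summary counts pharmacies as members of that network.

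A further objection concerns remedies. A reader might propose replacing X by a preference predicted from 2002 data on age, sex, literacy, marital status and city. That would test modification by demographics and city, which is a different question from the stated aim. Nor do the documents show that the same item was asked in 2002. The Protocol Summary says "The questionnaire addressed data on demographic and household characteristics, travel, migration, labor, health seeking behavior", but that sentence describes the face-to-face part, whereas hlthseek comes from the self-administered part. The DSMB report adds that question phrasing was modified for the outcome survey.

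**Conclusion.** The point holds as a risk built into the design of this secondary test. As written, b4 cannot separate effect modification from a change in subgroup membership, and nothing in the plan would show which has occurred.

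The size cannot be established from the documents. The OR range of about 0.71 to 1.22 rests on an assumed 30% pharmacy share, a 10 to 15 point net movement into the group, and movers' prevalence of 5% to 13% against 10%. Movement outwards reverses the direction. The rejection rates ignore between-city variation and are indicative only. The primary city-level analysis does not use hlthseek and is unaffected.

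**What to change.** 1. Add the 2006 city-level proportion naming a pharmacy as an outcome, compared between arms with the same paired regression as the other secondary endpoints. Adjust for the 2002 proportion if the same item was asked then. Report the result beside the interaction.
2. State in the plan that the interaction with 2006 hlthseek is associational, and is not a test of whether the intervention works better in people who prefer pharmacies.
3. Check whether the self-administered item was asked comparably in 2002. If so, add as a supportive analysis the interaction of treatment with each city's 2002 pharmacy share. Say plainly that it is ecological, rests on 20 cities and will be imprecise.

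The individual-level predicted-preference model should not replace the planned analysis.

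The cost is a few sentences in the plan, one further city-level model and possibly a second, all on data already collected or planned. The trial also has to make a more cautious claim for this secondary aim.

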NewSyph	Prevalence of elevated serum titer indicating recent syphilis infection	
Blood samples tested by RPR and confirmed by TPPA; result of each test is positive (titer <math>\geq</math> 1:8) or negative (titer < 1:8) and individual results are aggregated to the city level*.
 
GPS and FSW: Created variable in 2006 to accomplish this, using rpr, rpr dilution and tppa results.
	0 - 1	Outcome
HIVresul	Prevalence of HIV infection	
Blood sample tested by dual ELISA and confirmed by WB; result of each test is positive or negative and individual results are aggregated to the city level*
 
FSW: variable arrived as 0/1/5 (5= indeterminate) in 2006 with description: “hiv result”. Indeterminates treated as missing.
 
GPS: created variable to match above description, from separate wb and elisa results.
	0 - 1	Outcome
Tvresul	Prevalence of trichomonas infection	Urine samples tested by InPouch culture (baseline) or Aptima (2006); result of each test is positive or negative and individual results are aggregated to the city level* (female only)	0 - 1	Outcome
BV	Prevalence of bacterial vaginosis	??; result of each test is positive or negative and individual results are aggregated to the city level* (female only)	0 - 1	Outcome
CtGcSy	Prevalence of	GPS and FSW: Created from	0 - 1	Primary

	Chlamydia and/or gonorrhea and/or syphilis infection	ctresult, gresult, newsyph and aggregated to city level* If any of the 3 test results was missing, combined outcome treated as missing.		outcome
City	City code	assigned	1 - 20	
Arm	Randomization arm	assigned	0 = control 1 = intervention	Primary predictor
Pair	Randomization pair	assigned	1 - 10	Stratification variable
Age	Age (yrs)	GPS FF Q1.2		Covariate
Gender	Gender	GPS FF Q1.1	1=male 2=female	Covariate
Read	Can you read?	GPS FF Q1.4	1=yes 2=no 9=no response	
Married/Cohab	Marital status	GPS FF Q7.1	1=Single 2=Married 3=Cohabiting 4=Separated 5=Divorced 6=Widow/er 9=No response	
Eversex	Ever had sex:	GPS SA Q1.11 (female) Q1.12 (male)	0=no/1=yes	
Sexfsw	Sex w/prostitute:	GPS SA Q2.6 (males only, who replied 'yes' to 'eversex'),	0=no/1=yes	
Sexfswnum	How many times sex w/prostitute in last 12 months:	GPS SA Q2.9 (males only, who replied 'yes' to 'sexfsw')	0=None; 1-10=actual #; 11=more than 10; 66=doesn't remember	

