### Inferential analyses

#### *Primary analysis*

The unit of analysis will be the city (i.e. STI prevalence at the city level). This approach is appropriate since the sample size is approximately the same from city to city. The primary analysis of intervention efficacy will be based on the model

$$d_i^O = b_0 + b_1 d_i^B + \varepsilon_i \quad (M1)$$

where  $d_i^O$  is the difference in the primary STI endpoint (combined gonorrhea, chlamydia, trich in women, and syphilis prevalence) between the intervention and control communities (control – intervention) of the  $i$ 'th pair in the final (2006) outcome survey,  $d_i^B$  is the corresponding difference in the baseline survey and  $\varepsilon_i$  is a random error. The hypothesis of interest is

$$\begin{aligned} \text{Ho: } b_0 &= 0 && \text{(no intervention effect)} \\ \text{Ha: } \beta_0 &\neq 0 && \text{(intervention effect)} \end{aligned} \quad (H1)$$

Note that if  $d_i^B$  was not included in the model, this analysis would be equivalent to a paired t-test. The  $d_i^B$  term is included in the model to control for differences in STI prevalence at baseline (which may occur in spite of the matching).

Least squares regression will be used for model fitting. The standardized test statistic  $\hat{b}_0 / se(\hat{b}_0)$  from this analysis has a t-distribution with 8 degrees of freedom. A p-value will be reported for the hypothesis (H1) and a type I error rate ( $\alpha$ ) of 0.05 (two-tailed) will be used to reject/fail to reject the null hypothesis (H1).

The endpoint in the primary analysis will be **combsti** as measured in the GP.

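### The pharmacy-preference interaction pools men and women without Gender and T×Gender terms, so b4 can mix effect modification by sex with effect modification by pharmacy preference

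*Supplement*

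**What the plan says.** The last Data Analysis Plan in the Supplement, under Inferential analyses, Secondary analysis, describes the subgroup work this way: "we will use an individual level analysis of the 2006 GPS data based on the following model". The model is logistic. It holds an intercept, the treatment indicator T, city baseline prevalence B, the subset indicator X, the product T×X (coefficient b4) and a random city intercept. On outcome and test it says "The outcome in this analysis will be combsti" and "A two-sided 0.05 level test will be used".

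Two subsets are named. For use of sex workers the plan adds "and the analysis is restricted to men". For pharmacy preference the stated purpose is "To determine if the effectiveness of the intervention differs in individuals who prefer to use pharmacies for STI-related symptoms", with X = hlthseek; there is no restriction by sex and no sex term.

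The Primary analysis section describes the composite as "combined gonorrhea, chlamydia, trich in women, and syphilis prevalence", so the outcome has four components in women and three in men. The Variables table defines only the three-infection variable CtGcSy and has no row for combsti. The women-only trichomonas part is therefore read from the Primary analysis and Specific aims sections. Gender ("1=male 2=female") is listed there for use as a covariate, but no inferential model contains it. The DSMB report, item 10, asked for gender-specific analyses of each endpoint.

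**The concern.** Only women can show an effect on trichomonas, so the intervention's odds ratio on combsti may well differ between the sexes. The treatments differ by sex too: in the April 2006 trial summary (section 2.3), the pharmacy packet for women's discharge contains metronidazole and the men's packet contains two other antibiotics. Pharmacy preference may also differ by sex, because hlthseek asks about an abnormal secretion, which is a different symptom in men and in women.

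If both differ, the pharmacy-preferring and non-preferring groups hold different proportions of people with different treatment effects. A T×X contrast then appears even when preference itself modifies nothing. A significant b4 would be read as evidence about the pharmacy component, one of the two main parts of the intervention, in answer to a listed secondary aim.

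**Working it through.** **Plan figures.** The documents state no power or expected value for b4. The nearest figure is Table 2, Any STD in the general population, 30% reduction: power .99. With p1 = .10, p2 = .07, f = 500, k = .10, n = 10 and one-sided 5%, V = .10×.90/500 + .07×.93/500 + .01×(.0100 + .0049) = .000459. Power = Φ(√(8×.03²/.000459) − 1.645) = Φ(3.96 − 1.645) = .99, which reproduces it. This supports the prevalence scale and the 500 per city, but not the size of b4.

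**Inputs from the documents** (April 2006 trial summary, section 1.1): men, chlamydia 4.0% and gonorrhoea 0.3%; women, chlamydia 6.8%, gonorrhoea 0.8%, trichomonas 5.2%. The 2010 Protocol Summary (Laboratory methods) puts culture sensitivity at about 50% against the nucleic acid test, so .052/.5 ≈ .10 is a reasonable upper value for trichomonas.

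**Formula.** Let f_x be the share of women in group X = x, and P(t,x) = (1 − f_x)·p_men(t) + f_x·p_women(t). Without sex terms, and leaving out city effects, b4 = [logit P(1,1) − logit P(0,1)] − [logit P(1,0) − logit P(0,0)].

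**Step 1: when b4 is not biased.** Assume control prevalence 5.3% in men and 13.8% in women (the components summed, plus an assumed 1% syphilis), and no true modification by preference. Let the share of women be 60/40, 70/30 or 80/20 in non-preferers/preferers.

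- No intervention effect: b4 = 0 exactly.
- Odds ratio .65 in both sexes: b4 = .001, .002, .003, while b3 = −.20, −.40, −.60. The prevalence difference goes into b3.
- The same 30% relative reduction in both sexes: b4 = .006, .012, .018.
- Equal sex mix in the two groups: b4 = 0, whatever the effects.
- A true interaction of ln(.6/.9) = −.405 with no sex difference in effect: b4 is about −.40 at every mix.

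**Step 2: when it is biased.** Assume men .05 in both arms and women's other infections .075. Trichomonas is taken as independent of these and is the only infection affected. X = 1 means pharmacy first. There are 10,000 people (20 cities × 500, half of each sex).

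Worked case: trichomonas .10 halved, preference 60% in men and 30% in women. Women's composite is 1 − .925×.90 = .1675 in control and 1 − .925×.95 = .1213 in intervention cities (odds ratio .69). The share of women is .30/.90 = .333 in preferers and .70/1.10 = .636 in non-preferers.

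- Preferers: .0892 to .0738, logit change −.207.
- Non-preferers: .1248 to .0953, logit change −.302.
- b4 = −.207 + .302 = +.095.
- Cell sizes are 2,250 and 2,750 per arm, and SE = √Σ 1/(nP(1 − P)) = .140. Rejection = Φ(−1.96 + .68) + Φ(−1.96 − .68) ≈ .10.

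| Trichomonas, cut | Preference men/women (%) | b4 | SE | Rejection |
|---|---|---|---|---|
| .10, 50% | 45/35 | .03 | .14 | .06 |
| .10, 50% | 50/30 | .07 | .14 | .07 |
| .10, 50% | 60/30 | .10 | .14 | .10 |
| .10, 50% | 60/20 | .14 | .15 | .16 |
| .10, 50% | 30/50 | −.06 | .14 | .07 |
| .10, 70% | 60/30 | .15 | .14 | .18 |
| .052, 50% | 50/30 | .05 | .15 | .06 |
| .052, 50% | 60/30 | .07 | .15 | .07 |
| .052, 70% | 60/20 | .14 | .16 | .15 |

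The mildest corner (.052, 50%, 45/35) gives .02 and 5%. Stacking every extreme (.10, 70%, 60/20) gives .21 and 29%.

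**Step 3: check by simulation.** With 1,500 replicates, 20 cities × 250 men and 250 women, CV .10 and city effects, rejection without/with Gender and T×Gender was .07/.06 (50/30), .11/.05 (60/30), .16/.06 (60/20) and .08/.05 (30/50) with trichomonas .10 halved, and .19/.04 at 60/30 with a 70% cut.

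**Step 4: which terms are needed.** In the worked case, Gender as a main effect alone leaves b4 at .096. Gender plus T×Gender gives b4 = 0, and the SE rises from .140 to .147.

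**The case against.** A reader might infer that b4 measures the sex mix in place of pharmacy preference, or that any effect on trichomonas must surface as an interaction. Neither is supported. Step 1 shows that a true preference interaction is recovered and that a common odds ratio leaves b4 essentially untouched. Two conditions must hold together, and the documents establish neither. The intervention acts on several infections in both sexes, and a proportionate fall across them would give almost no bias. The larger figures need an effect on trichomonas alone and wide preference gaps. This stands, and it limits the size of the point.

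It can also be said that the aim is descriptive: whether effectiveness differs among people who prefer pharmacies, for whatever reason. On that reading the unadjusted contrast is the answer, and sex is only one of many correlates of preference. This stands in part. Sex differs from the other correlates because the outcome itself is defined differently for men and women, so even a descriptive contrast compares different mixtures of two outcomes.

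The plan also analyses trichomonas separately (tvresul, women only), and a dummy table attached to the preceding plan version tabulates pharmacy preference by gender. Both would help a careful reader notice the problem, but neither corrects the test of b4.

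**Conclusion.** The point holds as a possible, conditional bias of minor severity. The hlthseek model omits Gender and T×Gender, and b4 can then mix modification by sex with modification by pharmacy preference. The bias requires that preference and the intervention odds ratio both differ by sex. That is plausible because trichomonas is counted in women only, but the documents do not quantify it.

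Under the tabulated assumptions the bias is about .03 to .15 in absolute value, at most about one standard error, and the 5% test rejects in about 6 to 18% of trials. The sign depends on which sex prefers pharmacies. With infection as the outcome, a positive b4 means a smaller reduction among preferers. If preference is equal in the two sexes, or the odds ratio is the same, the bias is nil or negligible. The city-level primary analysis is not touched.

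**What to change.** In the Secondary analysis section, for X = hlthseek, add Gender and T×Gender to the model and test b4 in that model. Report the T-by-hlthseek estimate separately for men and for women alongside it. A Gender main effect alone is not enough, because the bias comes from the effect differing by sex. The sexfsw analysis needs no change, since it is already confined to men.

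The cost is one sentence in the plan, two more coefficients and a slightly wider interval for b4 (SE .140 to .147 in the worked case). No new data are needed, since Gender is already in the Variables table.
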